3.3 Secondary outcome (two medication adherence outcomes):

Medication adherence will be measured using filling patterns in pharmacy claims data for medications that qualified a patient for inclusion in the study.¹³ For each medication, we will create a drug supply diary linking all observed fills after initiation based on dispensing date and days' supply. Different drugs in the same chemically-related therapeutic class (e.g., sulfonylureas) will be considered to be interchangeable. We will allow for up to 180 days of carryover supply. From these supply diaries, we will calculate the proportion of days that patients had medications available to them, or the proportion of days covered (PDC), by dividing the number of days with medication available by the number of days during follow-up.¹⁴ If a patient loses continuous eligibility during the year after the index date, the PDC will be calculated based on the number of days available. If a patient loses continuous eligibility during the year after the index date, they will be censored on that date, and the PDC will be calculated based on the number of days available. In this PDC measurement, if patients had at least one antidiabetic medication available, then they will be considered to be adherent for that day. This definition allows for outcome measurement even when patients switch (e.g., switch from metformin to a sulfonylurea) or intensify therapy (e.g., adding a second oral diabetes medication or injectable medication).

Using this PDC measure, we will observe *1) the mean PDC in each study arm* and *2) the proportion of patients achieving optimal adherence* (defined by ≥ 0.80 PDC) as adherence outcomes in the follow-up period. In a sensitivity analysis of this outcome, medication adherence will be measured by calculating the PDC beginning from the first fill of a medication after assignment until the end of the 12-month follow-up. There will be no missing data for these outcomes, as previously described.

These outcomes will be analysed formally.

3.4 Secondary analyses:

Resource utilization:

As secondary analyses, we will also measure healthcare spending and healthcare resource utilization, including outpatient visits, emergency room visits, and hospitalizations, in the follow-up period in the medical and pharmacy claims data. Healthcare spending will be measured as total allowed amounts in

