the 12 months after randomization or until they lose continuous enrolment in both the medical and pharmacy claims files. This spending will sum the insurer paid amounts, coinsurance, copayments, and deductibles paid by patients. Healthcare resource utilization will be measured in the medical claims data. In specific, we will measure the count of outpatient office visits to providers, the count of emergency room visits, and the number of times each patient was hospitalized as outcomes from their randomization date until 12 months after randomization or until they lose continuous enrolment. These outcomes will be analysed formally.

Medication adherence:

Other medication adherence measurements will also be assessed descriptively, including adherence to each individual anti-diabetic medication, the proportion of patients who were adherent (defined by $\geq 80\%$ PDC), and gaps in medication availability. For these definitions, rates of switching, augmentation, discontinuation and other changes in prescription patterns will also be measured descriptively. Adherence to each diabetes medication will be measured using PDC, adjusting the denominator for new medication based on the number of days in the follow-up period that medication was used for. Persistence to medications will also be assessed, defined as a gap in supply of ≥ 60 days following exhaustion of the drug supply in the follow-up period. If insulin is used adjunctively or instead of oral therapy, persistence to insulin will also be measured. This approach to multiple medications has been used in other studies by our study group.^{3,15} These are planned to be measured descriptively.

Uptake of intervention:

We will also descriptively examine the number of follow-up calls and the number of patients who choose each type of decision (e.g., treatment intensification or adherence/lifestyle improvement). This will be based on de-identified call data provided by [REDACTED] (the pharmacists delivering the intervention).

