4.2 Analysis methods

4.2.1 Primary objective (Effectiveness of intervention):

Baseline characteristics:

We will measure key baseline characteristics in the 12-months prior to randomization in the pharmacy and medical claims data and enrolment files. These characteristics will include sociodemographic characteristics, such as age and sex, which will be measured in the enrolment files. We will also measure baseline clinical characteristics such as the presence of coronary artery disease, chronic obstructive pulmonary disease, asthma, hypertension, hyperlipidemia, congestive heart failure, depression, liver disease, chronic kidney disease, osteoporosis and prior macrovascular complications. These will be measured in medical claims files using ICD-10 codes. We will also measure the type of oral glucose-lowering agent used in the baseline period (e.g., medical class), average PDC at baseline, and whether or not the medication is branded. We will also measure patients' latest copayments for oral glucose-lowering agents in the baseline period. Finally, we will also measure baseline healthcare resource utilization variables as characteristics including the number of days hospitalized and the number of physician office visits.

We will report, in tabular format, the means and frequencies of baseline characteristics prior to assignment separately for patients in the intervention and control groups and compare these values using t-tests, chi-square tests, and their non-parametric analogues, as appropriate. We will provide absolute standardized differences between the two treatment groups.

Primary analyses:

Primary outcome (change in HbA1c): In the primary analysis, the primary outcome, mean change in glycemic control, will be compared using generalized estimating equations with an identity link function (as a continuous variable) and normally distributed errors within the imputed full analysis set, as described above. Data will be presented as the unadjusted absolute difference in the change in HbA1c between the groups along with 95% confidence intervals.

Secondary outcome (proportion achieving glycemic control)

1) *Proportion of patients achieving optimal glycemic control* (defined by HbA1c < 8): This outcome will be compared using generalized estimating equations with a logit link and binary distributed errors. Data will be presented as the unadjusted odds ratio for optimal glycemic control between the groups along with 95% confidence intervals.

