Secondary outcomes (medication adherence):

1) *Mean PDC in each study arm:* This outcome will be compared using generalized estimating equations with an identity link function and normally distributed errors. Data will be presented as the unadjusted absolute difference between the groups along with 95% confidence intervals.

2) *Proportion of patients achieving optimal adherence* (defined by ≥ 0.80 PDC): This outcome will be compared using generalized estimating equations with a logit link and binary distributed errors. Data will be presented as the unadjusted odds ratio for optimal adherence between the groups along with 95% confidence intervals.

Secondary analyses:

Healthcare resource utilization and spending: Secondary analyses of healthcare resource utilization will use a similar approach as the primary analysis among the full analysis set, except that we will use log link functions with Poisson errors to describe the count data. Health spending will also be evaluated with variances proportional to the mean (e.g., Poisson-like errors) using log-link functions in generalized estimating equations, which has been found to describe insurer healthcare spending data accurately based on prior research.⁵ Data will be presented as the unadjusted odds ratio along with 95% confidence intervals.

Adjusted analyses: If there are differences in baseline characteristics between study groups that are believed to be confounders (defined by a standardized mean difference of >0.1), we will repeat all of our analyses for the primary and secondary outcomes after adjusting for these covariates in multivariable regression. We will present these as adjusted effect estimates along with 95% confidence intervals.

Interactions: We will also explore any potential differences in effectiveness by the specific pharmacist delivering the intervention by evaluating effect measure modification and using interaction terms within the main model for the primary outcome of change in HbA1c. We will present p-values for interactions.

Subgroups: Subgroup analyses of the primary outcome (change in HbA1c) will also be performed for key subgroups, according to age, sex, depression, and baseline medication adherence levels. These analyses will be performed separately among subgroups of the characteristics and compared between the treatment arms. Data will be presented as unadjusted absolute differences in the change in HbA1c along with 95% confidence intervals.

Sensitivity analyses:

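### The main comparisons of office visits and spending are unadjusted, although each patient's prior use is measured or derivable from claims; prespecifying it would gain precision at little cost

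*SAP*

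**What the plan says.** **Outcomes.** SAP 3.4, under resource utilisation, defines "the count of outpatient office visits to providers, the count of emergency room visits, and the number of times each patient was hospitalized as outcomes", each counted from randomisation to 12 months or loss of enrolment. Spending is the total allowed amount over the same span. The section adds: "These outcomes will be analysed formally".

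**Model.** SAP 4.2.1, healthcare resource utilization and spending, opens with "Secondary analyses of healthcare resource utilization will use a similar approach as the primary analysis among the full analysis set". It specifies log-link generalised estimating equations with Poisson or Poisson-like errors, names no covariate, and ends: "Data will be presented as the unadjusted odds ratio along with 95% confidence intervals".

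**Baseline data.** SAP 4.2.1, baseline characteristics, covers the 12 months before randomisation in claims and enrolment files, and says "we will also measure baseline healthcare resource utilization variables as characteristics including the number of days hospitalized and the number of physician office visits". Emergency visits and spending are not named, though the list is open-ended. SAP 1.2 excludes only patients with under 3 months of prior continuous enrolment.

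**Adjustment rule.** SAP 4.2.1, adjusted analyses: for covariates believed to be confounders, defined by a standardised mean difference above 0.1, "we will repeat all of our analyses for the primary and secondary outcomes after adjusting for these covariates in multivariable regression".

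**Other use of baseline utilisation.** SAP 4.2.2 uses it as a predictor, but only in the prediction models.

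**The concern.** Patients who used much care last year tend to use much care this year. For frequent visits and for total spending, stable differences between patients can make up a good part of the outcome variance. A model with treatment arm alone leaves all of that in the error term. HbA1c at least brings in baseline through a change score; the utilisation and spending outcomes are follow-up totals, so following the primary analysis does not bring their baseline in.

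At stake is the width of the intervals for office visits and spending. A wider interval makes it more likely that a real difference is reported as none. Adjustment would not alter the question: with a log link and individual randomisation, the ratio of means is the same quantity with or without a baseline covariate.

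**Working it through.** **1. Is there a figure of the plan's own to reproduce?** Not for these outcomes. SAP 1.3 gives power for HbA1c and adherence and comments on the prediction models; it gives no power, variance or correlation for utilisation or spending. Everything in steps 3 to 5 is therefore a range under assumption.

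**2. Would the imbalance rule supply the adjustment?** With 700 per arm (SAP 1.3) and valid randomisation, the standardised difference of one baseline variable has standard error √(2/700) = 0.0535. The chance of exceeding 0.1 in either direction is

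2 × [1 − Φ(0.1/0.0535)] = 2 × [1 − Φ(1.87)] = 0.061.

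So the rule would leave out a given baseline utilisation measure about 94% of the time. Whether it acts depends on chance imbalance, not on how well the variable predicts the outcome.

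**3. Precision gained, analytic.** With correlation ρ between baseline and follow-up, adjustment multiplies the variance by 1 − ρ². Power for a comparison that has 80% unadjusted becomes Φ[(1.96 + 0.84)/√(1 − ρ²) − 1.96].

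| ρ (assumed) | Variance factor | SE reduction | Equivalent per arm, from 700 | 80% power becomes |
|---|---|---|---|---|
| 0.3 | 0.91 | 5% | 769 | 84% |
| 0.5 | 0.75 | 13% | 933 | 90% |
| 0.6 | 0.64 | 20% | 1,094 | 94% |

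**4. Precision gained, by outcome.** I simulated 700 per arm with complete 12-month windows, log-link Poisson regression and robust standard errors, with and without the log baseline value. Means and spread are assumptions, and the ranges cover weak to very strong stability of patient-level use.

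| Outcome | Assumed level | Observed correlation | SE reduction |
|---|---|---|---|
| Office visits | mean 8 a year | 0.37 to 0.76 | 7% to 35% |
| Spending | lognormal, log-scale SD 1.2 | 0.34 to 0.83 | 8% to 45% |
| Emergency visits | mean 0.3 a year | 0.13 to 0.28 | 1% to 4% |
| Hospitalisations | mean 0.12 a year | 0.06 to 0.14 | 0.2% to 1% |

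The upper ends for visits and spending need correlations near 0.8. At an observed correlation of 0.56 the reductions are 17% for visits and 20% for spending.

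**5. Truncated windows.** Baseline can be as short as 3 months (SAP 1.2), and follow-up stops at disenrolment (SAP 3.4). I took a count with mean 6 and correlation 0.5. With complete windows the SE reduction is 13%. I then truncated follow-up in 25% of patients (the loss rate in SAP 1.3) and, as an assumption, gave 30% of patients an annualised baseline of 3 to 12 months. The reduction fell to 8% when the model ignored follow-up time.

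**The case against.** The strongest reply is that this is a preference. Randomisation makes the unadjusted intention-to-treat comparison valid, nothing in the plan contradicts itself here, and these outcomes sit in its lowest tier: they are absent from the protocol's outcome lists and carry no power claim. All of that stands. It limits how much the point matters, but it is no reason to forgo a cheap gain in analyses that the SAP calls formal.

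Several stronger readings are tempting and are not supported:

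- **That the comparison is biased.** It is not; only precision is at issue.
- **That the SAP already measures baseline for all four outcomes.** It names two variables. Only office visits have a named, matching baseline. Days hospitalised is not the same measure as the number of hospitalisations, and emergency visits and spending would have to be derived.
- **That all four comparisons lose precision.** For the two rare outcomes the loss is close to nil.
- **That adjustment is ruled out unless imbalance appears, or that the rule excludes these outcomes.** Its wording covers primary and secondary outcomes, whereas utilisation and spending are listed as secondary analyses; yet the rule itself sits under that same heading. Its reach is ambiguous, not shown to stop short.
- **That adjustment would make these analyses conclusive.** For the mean-6 count in step 5 with complete windows, SE falls from 0.0305 to 0.0264. For a 5% difference in visits, log(1.05) = 0.0488, so power is Φ(0.0488/0.0305 − 1.96) = 36% unadjusted and Φ(0.0488/0.0264 − 1.96) = 46% adjusted. That helps, but is still low.

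**Conclusion.** The point holds as one of efficiency. The main utilisation and spending comparisons are unadjusted, prior office visits are already measured, and prior spending should be derivable from the same claims. For those two outcomes the standard error would fall by about 5% to 20% if the correlation lies between 0.3 and 0.6, and by less with truncated windows. The correlation is an assumption; the documents offer nothing to narrow it. For emergency visits and hospitalisations the gain is negligible at the assumed rates. The imbalance rule does not close the gap, because under randomisation it would rarely fire for a given measure. It would be wrong to infer that the planned results are invalid or that the improvement is free.

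**What to change.** In SAP 4.2.1, before the investigators receive the outcome data (SAP 2.2 places this after the late March 2018 lockout), prespecify that:

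- the main model for office visits includes log(1 + baseline office visits), and the main model for spending includes log(1 + baseline spending);
- each baseline value is scaled to enrolled months, because only 3 months of prior enrolment is required;
- robust standard errors are used, and the covariate enters whatever imbalance is observed;
- the matching baseline measure may optionally be added for emergency visits and hospitalisations;
- the unadjusted estimate is kept as supporting.

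**Cost:** a short SAP addition and a few lines of code, with no patient contact and no change to the ratio of means being estimated. Baseline spending must be derived from claims already due to be transferred, as must emergency visits if used, and the baseline window must be annualised.

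### SAP 4.2.1 labels ratios of means from log-link count and spending models as odds ratios, and states no term for enrolled time

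*SAP*

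**What the plan says.** SAP 3.4 (Resource utilization) defines the outcomes: counts of office visits, emergency room visits and hospitalisations, plus total spending. On spending it says: "This spending will sum the insurer paid amounts, coinsurance, copayments, and deductibles paid by patients". Utilisation is counted "from their randomization date until 12 months after randomization or until they lose continuous enrolment", and spending has the same cut-off. On their status it says: "These outcomes will be analysed formally".

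SAP 4.2.1 (Secondary analyses) gives the models. For utilisation, "we will use log link functions with Poisson errors to describe the count data". For cost, "Health spending will also be evaluated with variances proportional to the mean", again with a log link, in generalized estimating equations. The paragraph ends: "Data will be presented as the unadjusted odds ratio along with 95% confidence intervals".

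Elsewhere in SAP 4.2.1 the same effect measure goes with a different model. For the two binary outcomes (HbA1c below 8% and PDC of at least 0.80) the plan says "This outcome will be compared using generalized estimating equations with a logit link and binary distributed errors", and for adherence "Data will be presented as the unadjusted odds ratio for optimal adherence between the groups".

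The Protocol lists no utilisation or spending outcome, so the SAP is the only specification.

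**The concern.** There are two separate issues.

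**Effect measure.** The link and variance are stated clearly, but the reported quantity does not match them. A log-link model of a count or a cost does not produce an odds ratio. These outcomes are formally analysed, so the label decides how the published estimate is read.

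**Enrolled time.** A patient who leaves the plan early contributes fewer visits and less spending simply because observation stops. SAP 3.3 deals with this for PDC by dividing by the days available. SAP 3.4 and 4.2.1 give no offset, rate or annualisation for counts and spending. The statement that these analyses follow a similar approach to the primary one supplies none, because the primary model is an identity-link GEE without an exposure term. SAP 4.1 presents continuous data as means with standard deviations, so an arm mean of spending could be taken as a 12-month figure when it is a total over unequal follow-up.

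**Working it through.** The documents state no sample size, power or effect size for these outcomes, so there is no plan figure to reproduce. The check covers what the coefficient estimates and what unequal enrolled time does to it.

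**Step 1: what the coefficient is.** Let x = 1 for intervention and 0 for control.

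| Outcome (SAP 4.2.1) | Model | exp(b) | Label in SAP | Match |
|---|---|---|---|---|
| HbA1c <8%, PDC ≥0.80 | logit(p) = a + b·x | odds ratio | odds ratio | yes |
| Visit and hospitalisation counts | log(mean) = a + b·x | ratio of mean counts | odds ratio | no |
| Total spending | log(mean) = a + b·x | ratio of mean spending | odds ratio | no |

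A sum of payments has no event probability, so no odds exist for it.

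**Step 2: effect of enrolled time on the between-arm ratio.** Without an offset, exp(b) = true rate ratio × (T1/T0), where T is the mean enrolled fraction of the year in each arm. SAP 1.3 and Protocol 8.2 assume non-differential loss. Then T1 = T0 and exp(b) equals the true rate ratio.

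A simulation agrees. Its settings were 700 per arm, 25% loss in both arms, true ratio 1.0, an assumed 4 events per year with overdispersion, and 1,000 replicates.

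| Exit timing | Ratio without / with offset | Two-sided rejection without / with offset |
|---|---|---|
| Spread over the year | 1.00 / 1.00 | 5.5% / 5.1% |
| At 2.5 months | 1.00 / 1.00 | 5.6% / 6.4% |

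**Step 3: effect on the arm means.** T = 1 − d × (1 − t), where d is the share leaving and t is the leavers' mean observed fraction of the year. The shortfall against a full year is 1 − T.

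Inputs for d:
- About 0: SAP 1.3 expects no substantial loss for claims-based adherence.
- 0.15: the planning value in Protocol Table 6.
- 0.25: the SAP 1.3 planning rate for HbA1c, and the upper end of the Table 6 range.

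The documents do not give t. Two assumptions are used:
- Evenly spread exits: t = 0.5.
- Leavers observed 2.5 months on average: t = 2.5/12 = 0.208. The second is plausible because SAP 2.2 dates assignment to October and December 2016 and SAP 1.3 expects insurance changes mainly at calendar year end.

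| d | t | T | Shortfall |
|---|---|---|---|
| 0 | – | 1.000 | 0% |
| 0.15 | 0.5 | 1 − 0.15 × 0.5 = 0.925 | 7.5% |
| 0.25 | 0.5 | 1 − 0.25 × 0.5 = 0.875 | 12.5% |
| 0.25 | 0.208 | 1 − 0.25 × 0.792 = 0.802 | about 20% |

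For example, at an assumed 6 visits per year, 25% loss with evenly spread exits gives an arm mean of 6 × 0.875 = 5.25 visits, while the rate per person-year remains 6.

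**The case against.** The strongest reply is that the label is a wording carry-over. The link and variance stand in the same paragraph, so an analyst would fit the right model, and the estimate and interval would be unchanged. That is correct and limits the severity. It does not remove the point, because the sentence specifies what will be reported for formally analysed outcomes and nothing elsewhere corrects it.

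On enrolled time, the reply is that the SAP assumes equal loss in both arms, defines the observation window openly and promises no annualised figure. It also expects no substantial loss for claims-based adherence. Most of this stands. The last part carries over only partly: SAP 1.3 reasons that adherence can be calculated until eligibility ends, which works because PDC has a denominator of observed days. Counts and totals have none.

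Two stronger readings are tempting. A reader might infer that the missing offset biases the treatment comparison, for instance by setting the two ends of the loss range in Protocol Table 5 or Table 6 against each other as arm-specific rates. Those are planning ranges common to both arms, and both documents call the loss non-differential, so they give no basis for expecting a distorted ratio. A reader might also try to size the label error by converting between odds and risks. The plan analyses no binary event for these outcomes and gives no event frequency, so such a conversion would measure no error in the plan.

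**Conclusion.** Both parts hold, and together they are minor. The effect measure in SAP 4.2.1 is wrong as written for utilisation and spending; the chosen models are suitable and need no change of link or variance. The absence of a person-time term leaves the between-arm ratio unbiased as long as loss is non-differential, as the documents assume. Its consequence lies in the arm means, and the size cannot be fixed from the documents: it runs from about 0% to about 20% over the loss rates and exit timings considered, all of which are planning values for other outcomes or assumptions. These are secondary analyses, and the primary HbA1c analysis is not touched.

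**What to change.** In SAP 4.2.1, replace the odds ratio for these outcomes with a rate ratio for each of office visits, emergency room visits and hospitalisations, and a ratio of mean spending, each with its 95% confidence interval. Include log(enrolled days) as an offset, and report enrolled days and rates (or spending) per person-year by arm.

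The cost is a change of SAP wording and trivial programming, since enrolled days are already needed for the PDC denominator. There is one small downside to state in the SAP: the offset assumes that use and spending accrue in proportion to enrolled time and that loss is unrelated to the rate of use.
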